- For patients receiving therapeutic anticoagulation: stable anticoagulant regimen
- Negative HIV test at screening
- Negative hepatitis B surface antigen (HBsAg) test at screening
- Positive hepatitis B surface antibody (HBsAb) test at screening, or negative HBsAb at screening accompanied by either of the following:
 - Negative total hepatitis B core antibody (HBcAb)
 - Positive total HBcAb test followed by a negative (per local laboratory definition) hepatitis B virus (HBV) DNA test
- Negative hepatitis C virus (HCV) antibody test at screening, or positive HCV antibody test followed by a negative HCV RNA test at screening

The HCV RNA test will be performed only for patients who have a positive HCV antibody test.

- Negative Epstein-Barr virus (EBV) viral capsid antigen (VCA) IgM test or negative EBV polymerase chain reaction (PCR) test at screening

Patients with a positive IgM test or EBV PCR test are excluded.

- For women of childbearing potential: agreement to remain abstinent (refrain from heterosexual intercourse) or use contraception, and agreement to refrain from donating eggs, as defined below:

Women must remain abstinent or use contraceptive methods with a failure rate of $< 1\%$ per year during the treatment period, and for 90 days after the final dose of tiragolumab or placebo, 5 months after the final dose of atezolizumab, and for 6 months after the final dose of carboplatin and etoposide.

Women must refrain from donating eggs during this same period.

A woman is considered to be of childbearing potential if she is postmenarchal, has not reached a postmenopausal state (≥ 12 continuous months of amenorrhea with no identified cause other than menopause), and is not permanently infertile due to surgery (i.e., removal of ovaries, fallopian tubes, and/or uterus) or another cause as determined by the investigator (e.g., Müllerian agenesis). The definition of childbearing potential may be adapted for alignment with local guidelines or regulations.

Examples of contraceptive methods with a failure rate of $< 1\%$ per year include bilateral tubal ligation, male sterilization, hormonal contraceptives that inhibit ovulation, hormone-releasing intrauterine devices, and copper intrauterine devices.

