- History of idiopathic pulmonary fibrosis, organizing pneumonia (e.g., bronchiolitis obliterans), drug-induced pneumonitis, or idiopathic pneumonitis, or evidence of active pneumonitis on screening chest CT scan

History of radiation pneumonitis in the radiation field (fibrosis) is permitted.

- Known active tuberculosis
- Current treatment with anti-viral therapy for HBV or HCV
- Severe chronic or active infection within 4 weeks prior to initiation of study treatment, including, but not limited to, hospitalization for complications of infection, bacteremia, or severe pneumonia, or any active infection that, in the opinion of the investigator, could impact patient safety
- Treatment with therapeutic oral or IV antibiotics within 2 weeks prior to initiation of study treatment

Patients receiving prophylactic antibiotics (e.g., to prevent a urinary tract infection or chronic obstructive pulmonary disease [COPD] exacerbation) are eligible for the study.
- Significant cardiovascular disease, such as New York Heart Association cardiac disease (Class II or greater), myocardial infarction, or cerebrovascular accident within 3 months prior to randomization, unstable arrhythmias, or unstable angina

Patients with known coronary artery disease, congestive heart failure not meeting the above criteria, or left ventricular ejection fraction <50% must be on a stable medical regimen that is optimized in the opinion of the treating physician, in consultation with a cardiologist if appropriate.
- Major surgical procedure other than for diagnosis within 28 days prior to randomization or anticipation of need for a major surgical procedure during the course of the study
- Prior allogeneic bone marrow transplantation or solid organ transplant
- Any other diseases, metabolic dysfunction, physical examination finding, or clinical laboratory finding giving reasonable suspicion of a disease or condition that contraindicates the use of an investigational drug or that may affect the interpretation of the results or render the patient at high risk for treatment complications
- Patients with illnesses or conditions that interfere with their capacity to understand, follow, and/or comply with study procedures
- Treatment with any other investigational agent with therapeutic intent within 28 days prior to randomization
- Administration of a live, attenuated vaccine within 4 weeks before randomization or anticipation that such a live attenuated vaccine will be required during the study

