4.5.7 Laboratory, Biomarker, and Other Biological Samples

Samples for the following laboratory tests will be sent to the study site's local laboratory for analysis. Central laboratory analysis will be permitted only if local laboratory testing is not available.

- Hematology: WBC count with differential (neutrophils, eosinophils, basophils, monocytes, lymphocytes), RBC count, hemoglobin, hematocrit, platelet count, and differential count
- Chemistry panel (serum or plasma): bicarbonate or total carbon dioxide (if considered standard of care for the region), sodium, magnesium, potassium, calcium, chloride, glucose, BUN or urea, creatinine, total protein, albumin, phosphate, total bilirubin, ALP, ALT, AST, and LDH
- Coagulation: INR, and aPTT
- Thyroid function testing: thyroid-stimulating hormone, free triiodothyronine (T3) (or total T3 for sites where free T3 is not performed), and free thyroxine (also known as T4)

- HIV serology
- HBV serology: HBsAg, HBsAb, and total HBcAb for all patients; HBV DNA for patients with negative HBsAg and HBsAb tests and a positive total HBcAb
- HCV serology: HCV antibody and (if HCV antibody test is positive) HCV RNA
- EBV serology, including the following:
 - EBV VCA IgM
 - EBV PCR (if EBV VCA IgM test not available)
- Pregnancy test

All women of childbearing potential will have a serum pregnancy test at screening. During the study, urine pregnancy tests will be performed on Day 1 of every cycle, and after study treatment is discontinued (see [Appendix 1](#)). If a urine pregnancy test is positive, it must be confirmed by a serum pregnancy test.

- Urinalysis, including dipstick (pH, specific gravity, glucose, protein, ketones, blood)

The following samples will be sent to one or several central laboratories or to the Sponsor or a designee for analysis:

- Serum samples for tiragolumab and atezolizumab PK analysis through use of validated assays
- Serum samples for assessment of ADAs to tiragolumab through use of validated assays
- Serum samples for analysis of autoantibodies

Serum samples collected for the assessment of pharmacokinetics, ADAs, or biomarkers at baseline on Day 1 of Cycle 1 prior to the first dose of study treatment may be used for autoantibody testing if an immune-mediated adverse event develops in a patient that would warrant such an assessment.

- Pre-treatment tumor sample

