- ^l TSH, free T3 (or total T3 for sites where free T3 is not performed), and free T4 will be assessed \leq 96 hours before Day 1 of Cycles 1, 5, 9, and 13, and every fourth cycle thereafter. The Cycle 1 thyroid function testing does not need to be performed if the previous test was performed within the screening window.
- ^m All patients will be tested for HIV prior to the inclusion into the study and HIV-positive patients will be excluded from the study. Patients with active hepatitis B (chronic or acute; defined as having a positive HBsAg test result at screening) will be excluded from the study. Patients with past or resolved HBV infection (defined as the presence of HBcAb and absence of HBsAg) are eligible; HBV DNA should be obtained in these patients prior to randomization. Patients with HCV will be excluded from the study; patients who test positive for HCV antibody are eligible only if PCR is negative for HCV RNA. EBV serology samples will be collected at screening, and an EBV IgM test or EBV PCR test is required prior to randomization. Additional EBV serology tests will be performed for patients who subsequently experience an acute inflammatory event, such as systemic inflammatory response syndrome, while receiving study treatment.
- ⁿ Urinalysis by dipstick (specific gravity, pH, glucose, protein, ketones, and blood). Urinalysis is required at screening and will be obtained when clinically indicated.

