5.7 OTHER ANALYSES

5.7.1 Summaries of Conduct of Study

Study enrollment and major protocol deviations including major deviations of inclusion/exclusion criteria will be summarized by treatment arm for the FAS.

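### Does the mismatch between Appendix 1 and Sections 4.1.1 and 4.5.7 on who needs an HBV DNA test at screening call for a change to the plan?

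*Protocol*

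**What the plan says.** Three places in the protocol deal with HBV DNA at screening.

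- **Section 4.1.1 (Inclusion Criteria)** requires a negative HBsAg. It then requires "Positive hepatitis B surface antibody (HBsAb) test at screening, or negative HBsAb at screening accompanied by either of the following": a negative total HBcAb, or a "Positive total HBcAb test followed by a negative (per local laboratory definition) hepatitis B virus (HBV) DNA test". The DNA condition therefore sits inside the HBsAb-negative branch only.
- **Section 4.5.7 (Laboratory, Biomarker, and Other Biological Samples)** lists "HBV serology: HBsAg, HBsAb, and total HBcAb for all patients", and then "HBV DNA for patients with negative HBsAg and HBsAb tests and a positive total HBcAb". This is the same trigger as in Section 4.1.1.
- **Appendix 1, footnote m** defines past or resolved infection without reference to HBsAb: "defined as the presence of HBcAb and absence of HBsAg) are eligible; HBV DNA should be obtained in these patients prior to randomization". It names no DNA result that the patient must have. For hepatitis C the same footnote does name one: "patients who test positive for HCV antibody are eligible only if PCR is negative for HCV RNA".

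Section 4.1.2 adds general exclusions: clinically significant liver disease including active viral hepatitis, current anti-viral treatment for HBV, and "any active infection that, in the opinion of the investigator, could impact patient safety". On reporting, SAP Section 5.7.1 says that "major protocol deviations including major deviations of inclusion/exclusion criteria will be summarized by treatment arm for the FAS".

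**The concern.** Two sites could screen the same patient differently. A site working from the Schedule of Activities would order HBV DNA for an HBsAb-positive, HBcAb-positive patient. A site working from the inclusion criteria or the laboratory section would not. Sections 5.1.3 and 5.1.7 give viral reactivation as a reason for keeping patients with active infection out of the study, so a loose viral screening rule touches a stated safety rationale.

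Two further points add to the unease. Footnote m calls the whole HBcAb-positive, HBsAg-negative group eligible and omits the negative-DNA condition that Section 4.1.1 sets for its HBsAb-negative members. And a missing DNA result in the disputed profile departs from the footnote but not from Sections 4.1.1 or 4.5.7, so the same record could be logged as a deviation at one site and not at another, and deviations are reported by arm.

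**Working it through.** The plan has no figure to reproduce here. The check is to write each passage as a logical condition and run through the three markers, which give 2 × 2 × 2 = 8 profiles.

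Conditions for obtaining HBV DNA:

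- Section 4.1.1: HBsAg negative, HBsAb negative, HBcAb positive.
- Section 4.5.7: HBsAg negative, HBsAb negative, HBcAb positive.
- Footnote m: HBsAg negative, HBcAb positive, any HBsAb.

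| HBsAg | HBsAb | HBcAb | 4.1.1 | 4.5.7 | Footnote m | Same trigger? |
|---|---|---|---|---|---|---|
| − | − | − | no | no | no | yes |
| − | − | + | DNA, must be negative | DNA | DNA, result not stated | yes |
| − | + | − | no | no | no | yes |
| − | + | + | no | no | DNA, result not stated | **no** |
| + (4 profiles) | any | any | excluded | no | excluded | yes |

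The trigger agrees in 7 of 8 profiles and differs in 1, which is 1 of the 4 HBsAg-negative profiles.

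**The disputed profile (−, +, +).** Under Section 4.1.1 a positive HBsAb meets the criterion by itself. Footnote m also calls the patient eligible. The difference is whether a test should be obtained, not whether the patient may enter. One course of action satisfies all three passages: testing everyone in the wider group breaches none of them. A detectable result is not addressed by name, but as written Section 4.1.1 does not make entry depend on DNA in this profile, and the Section 4.1.2 exclusions leave the investigator grounds to keep a patient out.

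**The neighboring profile (−, −, +).** All three passages call for the test. Footnote m does not repeat the required result, but silence in a schedule footnote does not waive an inclusion criterion. Section 4.5.1 requires all eligibility criteria to be confirmed before randomization, so the condition in Section 4.1.1 still binds.

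**Where the result could enter the analysis.**

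- The analysis sets in SAP Section 4 rest on randomization, baseline brain metastases, receipt of study drug, and availability of PK or ADA samples. None depends on hepatitis serology, and there is no per-protocol set from which an eligibility deviation would remove a patient.
- The stratification factors are ECOG performance status and LDH.
- Screening comes before randomization and the study is double-blind, so the passage a site followed cannot depend on the arm assigned.
- The only output within reach is the deviation summary. It covers major deviations, and nothing in the documents classes a missed footnote test as major. A patient in the disputed profile without a DNA result still meets Section 4.1.1, so the missing test is no inclusion-criterion deviation.

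**Timing.** Version 6 gives the actual clinical cutoff for the primary analysis as 31 August 2023. Patients in the trial were screened before that date.

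**The case for a change.** The strongest case for acting is that footnote m carries real weight. Section 4.5 points to the Schedule of Activities and expects all its activities to be carried out and documented. Section 4.5.1 requires screening evaluations to be complete before randomization. On that reading the footnote adds a screening test that the eligibility section does not ask for, the subject is viral safety, and the correction costs a few words plus a listing of affected patients.

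The textual part of this stands: the passages differ, and no other passage settles the difference. The consequences are weaker.

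- *Safety rationale.* Sections 5.1.3 and 5.1.7 exclude active infection but set no DNA rule. Footnote m itself defines active hepatitis B by a positive HBsAg, which the disputed profile does not have.
- *Retrospective listing.* It would hold patients to a rule written after they were screened. A deviation should be judged against the protocol version in force at screening, and earlier versions are not among the documents.
- *Ease of counting.* Section 4.5.7 collects all three markers in every patient, but at local laboratories unless local testing is unavailable, and no visible passage says these results are entered on the eCRF. The cost of a listing is therefore not known to be small.

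Uneven logging of a minor deviation between sites remains possible. It would affect a descriptive record and no treatment comparison.

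**Conclusion.** The inconsistency is genuine and confined to 1 of 8 serology profiles. It concerns who should be tested, the passages can be followed together, and Section 4.1.1 settles eligibility in the same direction as the footnote for that profile. No endpoint, analysis set, stratification factor or event count depends on it.

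The conclusion rests on two assumptions. The first is that enrollment is complete, which is inferred from the cutoff date in Version 6 and not stated outright. The second is that a missing test in this profile would not be classed as a major deviation, on which the documents are silent. The number of patients in the profile is unknown because no prevalence is given.

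The three passages do need to be reconciled if the protocol is reopened or the wording reused. The choice of rule belongs to the sponsor's clinical team and is not judged here. For this trial, aligning the text now would alter no screening decision and no result, so no change to the plan follows.

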Appendix 1: Schedule of Activities

- For tiragolumab/placebo and atezolizumab, the initial dose will be administered over 60 (\pm 15) minutes. If the first infusion is well tolerated, subsequent infusions may be administered over 30 (\pm 10) minutes, respectively (see Sections 4.3.2.1 and 4.3.2.2). For carboplatin and etoposide, study drug will be administered as described in Section 4.3.2. Infusions should be given in the following order: atezolizumab → tiragolumab/placebo → carboplatin → etoposide.
- During the maintenance phase, infusions should be given in the following order: atezolizumab → tiragolumab/placebo. Additionally, during this phase, PCI is permitted as per local standard of care and will be reported on the Prophylactic Cranial Irradiation eCRF.
- CT scans (with oral/IV contrast unless contraindicated) or MRI scans of the chest and abdomen. A CT or MRI scan of the pelvis is required at screening and as clinically indicated or as per local standard of care at subsequent response evaluations. A CT (with contrast) or MRI scan of the head must be done at screening to evaluate CNS metastasis in all patients. See Section 4.5.6 for details.
- Perform every 6 weeks (\pm 7 days) for 48 weeks following Cycle 1, Day 1 and then every 9 weeks (\pm 7 days) thereafter, after completion of the Week 48 tumor assessment, regardless of treatment delays, until radiographic disease progression per RECIST v1.1 (or loss of clinical benefit for patients who continue study treatment after disease progression per RECIST v1.1), withdrawal of consent, death, or study termination by the Sponsor, whichever occurs first.
- If the patient discontinues study treatment for any reason other than radiographic disease progression per RECIST v1.1 (e.g., toxicity, symptomatic deterioration), tumor assessments will continue at the same frequency as would have been followed if the patient had remained on study treatment (i.e., every 6 weeks [\pm 7 days] for 48 weeks following Cycle 1, Day 1 and then every 9 weeks [\pm 7 days] thereafter) until radiographic disease progression per RECIST v1.1, withdrawal of consent, death, or study termination by the Sponsor, whichever occurs first, even if the patient starts another anti-cancer therapy after study treatment discontinuation. See Section 4.5.6 for details.
- Assessments and sample collections no longer required post clinical cutoff date for the primary analysis (actual date 31 August 2023). Upon reaching this milestone, no further data collection and analysis relating to these assessments is required for this study.
- All serious adverse events and adverse events of special interest, regardless of relationship to study drug, will be reported until █ days after the last dose of study drug or initiation of new systemic anti-cancer therapy after the last dose of study drug, whichever occurs first. All other adverse events, regardless of relationship to study drug, will be reported until █ days after the last dose of study drug or initiation of new systemic anti-cancer therapy after the last dose of study drug, whichever occurs first. After this period, all deaths should continue to be reported. In addition, the Sponsor should be notified if the investigator becomes aware of any serious adverse event or adverse event of special interest that is believed to be related to prior exposure to study treatment (see Section 5.6). These events should be reported using the Adverse Event eCRF.
- From 7 days before screening until the treatment discontinuation visit. All such medications should be reported to the investigator and recorded on the Concomitant Medications eCRF.

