5.3.1 Adverse Event Reporting Period

Investigators will seek information on adverse events at each patient contact. All adverse events, whether reported by the patient or noted by study personnel, will be recorded in the patient's medical record and on the Adverse Event eCRF.

After informed consent has been obtained, but prior to initiation of study treatment, only serious adverse events caused by a protocol-mandated intervention (e.g., invasive procedures such as biopsies, discontinuation of medications) should be reported (see Section 5.4.2 for instructions for reporting serious adverse events).

After initiation of study treatment, all adverse events will be reported until █ days after the final dose of study treatment or until initiation of new systemic anti-cancer therapy, whichever occurs first, and serious adverse events will continue to be reported until █ days after the final dose of study treatment or until initiation of new systemic anti-cancer therapy, whichever occurs first. In addition, adverse events of special interest will continue to be reported until █ days after the final dose of study treatment, regardless of initiation of new systemic anti-cancer therapy.

Instructions for reporting adverse events that occur after the adverse event reporting period are provided in Section 5.6.

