5.4 IMMEDIATE REPORTING REQUIREMENTS FROM INVESTIGATOR TO SPONSOR

Certain events require immediate reporting to allow the Sponsor to take appropriate measures to address potential new risks in a clinical trial. The investigator must report such events to the Sponsor immediately; under no circumstances should reporting take place more than 24 hours after the investigator learns of the event. The following is a list of events that the investigator must report to the Sponsor within 24 hours after learning of the event, regardless of relationship to study treatment:

- Serious adverse events (defined in Section 5.2.2; see Section 5.4.2 for details on reporting requirements)
- Adverse events of special interest (defined in Section 5.2.3; see Section 5.4.2 for details on reporting requirements)
- Pregnancies (see Section 5.4.3 for details on reporting requirements)

For serious adverse events and adverse events of special interest, the investigator must report new significant follow-up information to the Sponsor immediately (i.e., no more than 24 hours after becoming aware of the information). New significant information includes the following:

- New signs or symptoms or a change in the diagnosis
- Significant new diagnostic test results
- Change in causality based on new information
- Change in the event's outcome, including recovery
- Additional narrative information on the clinical course of the event

Investigators must also comply with local requirements for reporting serious adverse events to the local health authority and IRB/EC.

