Appendix 1: Schedule of Activities

Procedure	Screening	All Treatment Cycles ^a		Treatment Discontinuation Visit ≤30 Days after Last Dose of Study Treatment	Survival Follow-Up
	Days –28 to –1	Induction Phase (Cycles 1–4)	Maintenance Phase (Starting from Cycle 5)		Every 3 Months after Disease Progression
		Every 21 Days (±3 Days) ^b	Every 21 Days (±3 Days)		
Adverse events	x	x	x	x ^u	x ^u
Cancer-related procedures (medical, surgical, and radiation)		x	x	x	x
Concomitant medications	x ^v	x ^v	x ^v	x ^v	
Patient-reported outcomes (EORTC QLQ-C30, EORTC IL46, PRO-CTCAE [select items], and EQ-5D-5L) ^w		x ^{t, w}	x ^{t, w}	x ^{t, w}	x ^{t, w}
Survival and anti-cancer therapy follow-up					x ^{t, x}

CE = carboplatin and etoposide; CT = computed tomography; EBV = Epstein-Barr virus; ECOG = Eastern Cooperative Oncology Group; eCRF = electronic Case Report Form; EORTC = European Organisation for Research and Treatment of Cancer; EQ-5D-5L = EuroQoL 5 Dimensions 5-Level Version; HBcAb = hepatitis B core antibody; HBsAg = hepatitis B surface antigen; HBV = hepatitis B virus; HCV = hepatitis C virus; MRI = magnetic resonance imaging; non–small cell lung cancer; PCI = prophylactic cranial irradiation; PCR = polymerase chain reaction; PD = pharmacodynamic; [REDACTED] PRO = Patient-Reported Outcome; QLQ-C30 = Quality-of-Life Questionnaire Core 30; PRO-CTCAE = Patient-Reported Outcomes of the Common Terminology Criteria for Adverse Events; RECIST = Response Evaluation Criteria in Solid Tumors; SCLC = small cell lung cancer; TSH = thyroid-stimulating hormone.

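### The Appendix 1 adverse event footnote stops AESI reporting at new systemic anti-cancer therapy, while Protocol Sections 5.3.1 and 5.4.2.2 continue it to the day limit regardless (minor)

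*Protocol*

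**What the plan says.** **Appendix 1, Schedule of Activities.** The adverse event row carries a footnote (u, by its place in the sequence) in the treatment discontinuation and survival follow-up columns. It reads "All serious adverse events and adverse events of special interest, regardless of relationship to study drug, will be reported until" a redacted number of "days after the last dose of study drug or initiation of new systemic anti-cancer therapy after the last dose of study drug, whichever occurs first". A later sentence of the same footnote sets a duty after that period, citing Section 5.6: the Sponsor should be told of "any serious adverse event or adverse event of special interest that is believed to be related to prior exposure to study treatment".

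**Section 5.3.1.** Adverse events in general are reported to a redacted day limit "or until initiation of new systemic anti-cancer therapy, whichever occurs first, and serious adverse events will continue to be reported until" a further redacted limit, again with the new-therapy cutoff. AESIs then have their own sentence. They continue until a redacted number of "days after the final dose of study treatment, regardless of initiation of new systemic anti-cancer therapy".

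**Section 5.4.2.2.** It repeats the pattern in the same terms: SAEs end at the earlier of the day limit and new therapy, and AESIs run to the day limit regardless.

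**Section 5.6.** After the reporting period, all deaths are reported, along with any SAE believed related to earlier study treatment. AESIs appear only in the clause that describes the period and in the title of the paper form.

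**The concern.** Sections 5.3.1 and 5.4.2.2 deliberately take AESIs out of the new-therapy cutoff. The footnote names AESIs and applies that cutoff to them, which is more than an omission. The footnote sits on the schedule at the visits after treatment ends, which is where a patient may begin another therapy. A site reading its duties from the schedule could close AESI reporting earlier than the body text allows.

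What is at stake is completeness of safety reporting for one event class in one interval. No efficacy endpoint is touched.

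**Working it through.** No stated figure needs reproducing. The check sets the rules side by side.

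| Source | Rule for AESIs | Does new therapy end reporting? |
|---|---|---|
| Section 5.3.1 | Own sentence, to the day limit | No |
| Section 5.4.2.2 | Own sentence, to the day limit | No |
| Appendix 1 footnote | Grouped with SAEs | Yes, if earlier than the day limit |

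**Does redaction matter?** Measure time from the last dose. Let N be the start of new therapy, B the day limit in the body text and F the day limit in the footnote. B and F are both redacted and may differ.

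- Body text: AESI reporting ends at B.
- Footnote: AESI reporting ends at min(N, F).
- If N < B, then min(N, F) ≤ N < B, so the footnote always ends earlier.
- The gap is B − min(N, F), which is at least B − N and so greater than 0, whatever F is.

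The conflict therefore exists for any patient who starts new therapy before B. Its length and frequency cannot be computed: B and F are hidden and the documents give no distribution for N.

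**Which events fall in the gap?** Take an AESI known to the investigator, with onset after N and before B.

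1. Sections 5.3.1 and 5.4.2.2 require it, with no condition on relatedness.
2. Under the footnote the reporting period is over. If the event is believed related to earlier study treatment, the after-period sentence still captures it.
3. If it is judged unrelated, the footnote requires nothing.

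The possible loss is thus confined to unrelated AESIs. Table 6 in Section 5.3.4 narrows it further, because an event counts as related unless there is evidence for another cause or no plausible timing.

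**Is the rule still live in Version 6?** Appendix 1 has a separate footnote, "Assessments and sample collections no longer required post clinical cutoff date for the primary analysis", which records 31 August 2023 as the actual date. It is attached to the row "Survival and anti-cancer therapy follow-up" but not to the adverse event row, so adverse event reporting is not expressly cancelled. However, Section 4.6.1 limits follow-up activities to the period up to that date, the survival follow-up footnote in Appendix 1 says the same of survival information, and Section 4.6.2 gives patients already in survival follow-up a closing visit or call. Section 4.5.6 keeps patients on treatment under limited follow-up. The conflict can therefore reach only patients who later stop study treatment and start new therapy inside the window, at a stage with little scheduled contact.

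**After-period wording.** The footnote covers related SAEs and AESIs, and Section 5.6 covers related SAEs. A site that follows the broader footnote also satisfies Section 5.6. Serious AESIs are covered by both, so the difference concerns non-serious AESIs only. How many there are cannot be judged, because the list in Section 5.2.3 is redacted.

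**The case against.** The strongest reply is that Section 5 already directs safety reporting. Sections 5.1 and 5.3 send investigators to its subsections, and Sections 5.3.5.8 and 5.6 take the reporting period from Section 5.3.1. With two body sections in agreement, the footnote looks like a loose summary that few would act on. This marks the footnote as the outlier. It does not cure the conflict, because no precedence clause was found and the footnote's only cross-reference, to Section 5.6, follows its after-period sentence and not its stopping rule. For the same reason it would go too far to say that the body text formally governs.

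A second reply is that nothing measurable follows. That largely stands and is why the point is minor.

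Three stronger readings are tempting, and the documents do not support them.

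- **Section 5.4 proves the footnote wrong.** Section 5.4 requires reports "within 24 hours after learning of the event, regardless of relationship to study treatment", but it sets the speed of reporting and lists SAEs and AESIs alike, with no window. Read as a timing rule, it would also extend SAE reporting past new therapy, which Sections 5.3.1 and 5.4.2.2 deny. Only those two sections support the point.
- **The rules for SAEs and other adverse events agree fully.** Both texts use a new-therapy cutoff for these classes, but the footnote counts only therapy begun after the last dose of study drug, and the day limits are hidden. The practical gap is probably small, since Section 4.6.1 requires study treatment to stop when other anti-cancer therapy is used. Full agreement still cannot be confirmed.
- **The Section 5.6 mismatch is a second data loss.** It is a difference in breadth, and both texts can be satisfied at once.

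**Conclusion.** Wrong as written, minor. Appendix 1 and Sections 5.3.1 and 5.4.2.2 give incompatible AESI stopping rules, and this is certain from the visible wording. The size is not computable. The only reports at risk are AESIs known to the investigator, occurring after new therapy but inside the day window, and judged unrelated.

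A reader might infer that the safety comparison is biased or the AESI tables incomplete. The documents do not show this. Nothing suggests that the arms would be affected differently. SAP Section 5.6.2 builds its AESI summaries from MedDRA-based groupings of the adverse event database, and because the protocol's own AESI list is redacted, the overlap cannot be checked. Nor is a wider effect on current patients shown: those on treatment are untouched until they stop and start something new. Only Version 6 is available, so nothing can be said about the wording under which earlier data were collected.

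**What to change.** 1. Reconcile the Appendix 1 footnote with Sections 5.3.1 and 5.4.2.2 so that one AESI stopping rule applies throughout. Since the two body sections agree, the simplest edit is to take AESIs out of the footnote's joint sentence and give them their own sentence matching those sections.
2. As a secondary wording point, make Section 5.6 and the footnote cover the same event classes after the reporting period.
3. Notify sites by clarification letter or in the next amendment.

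The cost is one footnote sentence and one phrase for the after-period wording. No visits, data fields or analyses are added. No retrospective query is proposed, because the wording of earlier versions cannot be checked.
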